7.7.3 Time to Progression (TTP)

TTP is defined as number of days between start of treatment to the first documentation of disease progression. TTP will be re-calculated whenever the baseline is reset due to addition of new anti-cancer therapy or increase of carfilzomib dose/frequency:

- 1) For regimens that continue from initial study without baseline being reset, if subjects didn't progress before PX-171-010, then TTP for the period from initial study to PX-171-010 study will be calculated as Date of Disease Progression – Date of first dose in initial study + 1 day, and TTP for the period of PX-171-010 study only will be calculated as Date of Disease Progression – Date of first dose in PX-171-010 + 1 day.
- 2) For regimens that start in PX-171-010 study with baseline being reset from initial study or previous regimens, TTP will be calculated as Date of Disease Progression – Date of first dose in the first regimen among the regimens with common baseline + 1 day. The same censoring rules, except for death, as in analysis of PFS ([Section 7.7.2](#)) will be applied in calculation of TTP. Subjects who die before disease progression will be censored at death date.

The number and percentage of subjects with events, the number and percentage of subjects censored will be calculated. Kaplan-Meier method will be used to estimate the distribution of TTP for each disease cohort by regimens. The 25%, 50% and 75% KM quartiles will be provided along with a two-sided 95% confidence interval ([Klein and Moeschberger, 1997](#)).

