9.3.1 DISEASE PROGRESSION

Discontinuation of treatment due to either progression or deterioration due to the primary malignancy should be recorded on the Treatment Discontinuation CRF as "Disease Progression" and not as an AE or an SAE, unless the event meets the SAE reporting criteria described in [Section 9.4](#).

In addition to an increase in M-protein, natural disease progression of multiple myeloma typically displays specific clinical signs and symptoms such as elevated Calcium, Renal insufficiency, Anemia, and Bone disease (known as the “CRAB” features) (Durie 2006). Signs and symptoms clearly associated with progression should not be listed as AEs unless judged by the Investigator to be atypical or accelerated or if the Investigator considers the sign or symptom to be caused by the study drug. If there is any uncertainty regarding causality, the event should be recorded in the CRF as an AE or SAE as appropriate.

All deaths during treatment or within 30 days of the last dose of study drug are to be reported as SAEs (see Section 9.4). The corresponding entry for progression-related deaths on the AE CRF should use the verbatim term “Disease Progression” rather than the specific sign or symptom that may have been the immediate cause of death. Additional details of the event (such as the primary and contributory causes of death) should be reported on the Death CRF.

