APPENDIX E: RESPONSE CRITERIA FOR SOLID TUMORS

Evaluation of Target Lesions	
Complete Response (CR):	Disappearance of all target lesions
Partial Response (PR):	At least a 30% decrease in the sum of the LD of target lesions, taking as reference the baseline sum LD
Progressive Disease (PD):	At least a 20% increase in the sum of the LD of target lesions, taking as reference the smallest sum LD recorded since the treatment started or the appearance of one or more new lesions
Stable Disease (SD):	Neither sufficient shrinkage to qualify for PR nor sufficient increase to qualify for PD, taking as reference the smallest sum LD since the treatment started
Evaluation of Non-Target Lesions	
Complete Response (CR):	Disappearance of all non-target lesions and normalization of tumor marker level
Incomplete Response/ Stable Disease (SD):	Persistence of one or more non-target lesion(s) or/and maintenance of tumor marker level above the normal limits
Progressive Disease (PD):	Appearance of one or more new lesions and/or unequivocal progression of existing non-target lesions ¹

¹ Although a clear progression of “non target” lesions only is exceptional, in such circumstances, the opinion of the treating physician should prevail and the progression status should be confirmed later on by the review panel (or study chair).

Evaluation of Best Overall Response

The best overall response is the best response recorded from the start of the treatment until disease progression/recurrence (taking as reference for PD the smallest measurements recorded since the treatment started). In general, the subject's best response assignment will depend on the achievement of both measurement and confirmation criteria.

Target Lesions	Non-Target Lesions	New Lesions	Overall Response
CR	CR	No	CR
CR	Incomplete Response/SD	No	PR
PR	Non-PD	No	PR
SD	Non-PD	No	SD
PD	Any	Yes or No	PD
Any	PD	Yes or No	PD
Any	Any	Yes	PD

- Subjects with a global deterioration of health status requiring discontinuation of treatment without objective evidence of disease progression at that time should be classified as having “symptomatic deterioration.” Every effort should be made to document the objective progression even after discontinuation of treatment.

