7.7.1 Overall Survival (OS)

Duration of OS is defined as the days from the start of treatment (initial study) to death due to any cause. For subjects who are alive at the time of the data cut-off, duration of OS will be censored as of the date the subject was last known to be alive.

Since the subjects will be followed up till 30 days after administration of last dose of study drug only per protocol, OS will be calculated and presented in a listing, no Kaplan-Meier estimates will be provided. Number and percentage of subjects who died within 30 days after administration of last dose of study drug will be calculated and death reason will be summarized.

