7.7.2 Progression Free Survival (PFS)

PFS is defined as number of days between start of treatment and first evidence of documented disease progression or death (due to any cause), whichever occurs first. Disease progression will be determined by the local investigator for regimens with the same baseline using the International Uniform Response Criteria ([Durie et al. 2006, with corrections](#)) (IMWG-URC) for multiple myeloma subjects and RECIST criteria ([Therasse et al. 2000](#)) for solid tumor subjects. PFS will be re-calculated whenever the baseline is reset due to addition of new anti-cancer therapy or increase of carfilzomib dose/frequency:

- 1) For regimens that continue from initial study without baseline being reset, if subjects didn't progress before PX-171-010, then PFS for the period from initial study to PX-171-010 study will be calculated as Disease Progression /Death Date – Date of first dose in initial study + 1 day, and PFS for the period of PX-171-010 study only will be calculated as Disease Progression /Death Date – Date of first dose in PX-171-010 + 1 day.
- 2) For regimens that start in PX-171-010 study with baseline being reset from initial study or previous regimens, PFS will be calculated as Disease Progression /Death Date –

Date of first dose in the first regimen among the regimens with common baseline + 1 day.

PFS will be right-censored for subjects who met one of the following conditions: 1) no baseline disease assessments or any post-baseline assessments, 2) alive and does not have documentation of disease progression before a data analysis cutoff date. The PFS censoring rules are described in Table 1.

Table 1. Censoring Rules for PFS Analysis

Situation	Date of Progression or Censoring	Outcome
No baseline disease assessments or any post-baseline assessments	Date of first dose	Censored
Alive and without documentation of disease progression	Date of last disease assessment	Censored
Death or disease progression between planned disease assessments	Date of death or first disease assessment showing disease progression, whichever occurs first	Progressed
Death or PD immediately after more than 1 consecutively missed disease assessment visit*	Date of last disease assessment before the first missed visit	Censored
Death before first disease assessment	Date of death	Progressed

* If death or PD is more than 168 days after previous disease assessment, or the first dosing date if there is no previous disease assessment.

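### Failures that the CRF records as Disease Progression but that lack criteria-based PD are censored in TTP (and, for living withdrawals, in PFS), which biases these times upward

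*SAP*

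**What the plan says.** **Event and censoring rules.** SAP 7.7.3 defines the endpoint by documentation: "TTP is defined as number of days between start of treatment to the first documentation of disease progression". It takes over the PFS censoring rules except for death, and for death it says "Subjects who die before disease progression will be censored at death date", whatever the cause. SAP 7.7.2 has the local investigator judge progression by the International Uniform Response Criteria (myeloma) or RECIST (solid tumors). The PFS event there is "first evidence of documented disease progression or death (due to any cause), whichever occurs first". In Table 1 of that section, the row "Alive and without documentation of disease progression" censors at the last disease assessment, and through 7.7.3 this row also governs TTP. Protocol 10.4.2 likewise censors subjects who finish without documented progression at their last assessment.

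**What the CRF records.** Protocol 9.3.1 says of withdrawals: "Discontinuation of treatment due to either progression or deterioration due to the primary malignancy should be recorded on the Treatment Discontinuation CRF", under the label Disease Progression. Of deaths it says: "The corresponding entry for progression-related deaths on the AE CRF should use the verbatim term", namely Disease Progression, with primary and contributory causes on the Death CRF.

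**Chance of later documentation.** Disease is assessed at Cycle 3 and every 3 cycles (Protocol 7.6), at least every 3 months (7.8), and once at end of study, within 30 days of the last dose and before new therapy (7.7). SAP 7.7.1 notes that "subjects will be followed up till 30 days after administration of last dose of study drug only per protocol". For solid tumors, Protocol Appendix E recognises symptomatic deterioration without objective progression and adds: "Every effort should be made to document the objective progression even after discontinuation of treatment". No later visit is scheduled for this.

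**The concern.** Two groups of subjects have, in the investigator's recorded judgement, failed because of their cancer, yet the analysis treats them as not having failed:

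- subjects who die of progression before any assessment meets the criteria (TTP only, since PFS counts the death);
- living subjects who stop for deterioration due to the malignancy without criteria-based progression (TTP and PFS).

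Kaplan-Meier estimation assumes that a censored subject has the same future risk as those still under observation. Here the reason for leaving is the failure itself, so the assumption breaks in a known direction and the estimated times are too long. The study tests no hypotheses (Protocol 10.1). The Kaplan-Meier quartiles and their 95% confidence intervals are therefore themselves the efficacy result, and a bias in them goes straight into what is reported.

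**Working it through.** **Design figures.** The documents give no expected TTP, event count or share of undocumented failures, so there is no planned figure to reproduce. The one related number checks: 2 missed assessments x 3 cycles x 28 days = 168 days, the threshold in the Table 1 footnote.

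**How each case is classified under the text.**

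- Withdrawn for PD shown by a test or procedure: event in TTP and PFS, dated at that test (Protocol 8).
- PD first shown at the end-of-study assessment: event in both.
- Progression-attributed death, no earlier criteria-based PD: PFS event (subject to the 168-day rule), TTP censored at death.
- Alive, stopped for deterioration, no criteria-based PD: censored at the last assessment in both.

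Only the last two are at issue.

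**Closed form.** Assume exponential progression times with hazard λ, and a constant share p of true progressions censored at the moment of failure. The hazard that Kaplan-Meier recovers is (1-p)λ. The estimated median is ln 2 / ((1-p)λ), which is 1/(1-p) times the true median.

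**Simulation on a visit grid.** The setting was 400,000 subjects assessed every 84 days (3 x 28). Documented PD was dated at the next visit. Undocumented deaths were censored at death, and undocumented withdrawals at the last visit. Independent other discontinuation had a median of 720 days. True median TTP was set to 360 or 180 days. All these rates are assumptions. The table gives the proportion progression-free at day 336 under the SAP rule, then with the undocumented cases counted as events.

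| p | 1/(1-p) | Median 360 d: SAP / counted | Median 180 d: SAP / counted |
|---|---|---|---|
| 5% | 1.05 | 0.526 / 0.510 (+1.6 points) | 0.277 / 0.261 (+1.6) |
| 10% | 1.11 | 0.543 / 0.510 (+3.3) | 0.293 / 0.261 (+3.2) |
| 20% | 1.25 | 0.578 / 0.510 (+6.8) | 0.330 / 0.261 (+6.9) |
| 30% | 1.43 | 0.616 / 0.510 (+10.6) | 0.373 / 0.261 (+11.2) |

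At p = 0 the two rules agree (0.510 and 0.261), so the differences come from the censoring rule alone.

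**PFS.** Only the withdrawals matter. With true median 360 days and p = 20%, PFS at day 336 is 0.510 if all undocumented cases are deaths (no bias), 0.542 if half are withdrawals and 0.578 if all are.

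**A caution.** Simulated medians move in 84-day steps. At p = 20% and true median 360 days they are 504 days under the SAP rule and 386 days with the cases counted. Part of that gap comes from the visit grid and from dating events at discontinuation or death, so it should not be read as the bias.

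**The case against.** **The affected group may be small.** Protocol 8 requires source documentation of progression and dates it by the test. The end-of-study assessment catches further cases. Assessments may be more frequent than every 3 months. For myeloma, criteria-based PD already includes attributable hypercalcaemia and new or enlarging bone lesions or plasmacytomas (Appendix D). Treatment may also continue after progression, so a death or withdrawal coded as progression may follow a PD that has already been counted. All this stands. A reader might infer that every death or withdrawal carrying the Disease Progression label is censored; the documents do not support that.

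**Requiring objective PD is a deliberate choice.** Appendix E separates symptomatic deterioration from PD, and censoring deaths from other causes is the usual TTP convention. This also stands, and it is why the withdrawals belong in a sensitivity analysis. It does not justify censoring a death that the investigator attributes to progression without showing the effect.

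**The SAP does not say how the CRF label maps to the event.** SAP 7.7 refers only to the investigator's assessment on the CRF page, so a programmer might count a progression-coded death as progression. The text of 7.7.2 and 7.7.3, with events defined by documentation and the response criteria, points to censoring. If both readings are open, two programmers could obtain different event counts, and the same clarification is needed.

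**PFS already counts the deaths.** True, subject to the 168-day rule, so comparing PFS with TTP shows part of the effect. PFS still censors the deterioration withdrawals.

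**Conclusion.** The point holds for subjects with no criteria-based PD on record. For them the stated rules censor informatively: progression-attributed deaths in TTP, and living deterioration withdrawals in TTP and PFS. The direction, toward longer times, is clear. The size is not, because it rests wholly on the share of undocumented failures, which the documents do not give. Under the exponential assumption the median inflation runs from none at p = 0 through 5% at p = 5% to 25% at p = 20%. For withdrawals the formula is approximate, because they are censored at the earlier last assessment.

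A reader might also expect the table of termination reasons (SAP 7.2) to show more progression than the TTP and PFS event counts. That does not follow. PFS events include deaths from any cause, PD with continued treatment is an event without a termination, and the counts are made by regimen.

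TTP and PFS are descriptive secondary endpoints, so this is a change worth making and not a threat to the primary safety objective.

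**What to change.** **SAP 7.7.3.** Censor only deaths from causes other than disease progression. Count a death whose AE verbatim term or Death CRF cause is Disease Progression as a TTP event on the date of death, subject to the same 168-day missed-assessment rule as PFS. Keep the version that censors all deaths as a sensitivity analysis. The reverse assignment of main and sensitivity analysis is also acceptable, provided both are prespecified.

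**SAP 7.7.2 and 7.7.3.** Add a sensitivity analysis in which a Treatment Discontinuation CRF reason of Disease Progression, without criteria-based PD, is an event on the discontinuation date.

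**Reporting.** Give the number of such deaths and withdrawals by disease cohort. If it is zero, nothing changes; if not, readers can judge the effect.

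**Cost.** A few sentences in the SAP and one or two extra runs on fields already collected. The analysis will rely on investigator-judged cause, as all progression in this study already relies on the investigator. Where such cases exist, TTP and PFS will come out somewhat shorter.

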7.7.4 Additional Efficacy Analyses

7.7.4.1 Objective Response Rate (ORR)

Best overall response will be determined by the local investigator for regimens with the common baseline using the International Uniform Response Criteria ([Durie et al. 2006, with corrections](#)) (IMWG-URC) and the European Group for Blood and Marrow Transplant (EBMT) criteria ([Bladé et al. 1998](#)) for multiple myeloma subjects and RECIST criteria ([Therasse et al. 2000](#)) for solid tumor subjects.

Objective response rate (ORR) is defined according to disease cohort:

- MM - ORR is defined as proportion of subjects for whom the best overall response is stringent complete response (sCR), complete response (CR), very good partial response (VGPR), or partial response (PR).

- Solid Tumor – ORR is defined as the proportion of subjects for whom the best overall response is confirmed PR or confirmed CR.

Point estimates for ORR will be accompanied by 2-sided 95% confidence intervals ([Clopper CJ and Pearson, 1934](#)).

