5.5 Baseline

If subjects had not received other anti-cancer therapies and not reached progressive disease when they enrolled in study 010, baseline disease assessments from the initial study will be used for baseline values for determining response and progression unless no prior assessments were collected (eg, PX-171-008). For those subjects who didn't have baseline collected in prior study, tumor assessments will be conducted at the time of screening for the current study using the appropriate method. And for those who received other anti-cancer therapies and/or progressive disease when they enrolled in study 010, baseline values from current study will be used.

During the study, the addition of certain approved agents with known antitumor activity or increase of carfilzomib dose and/or frequency is permitted if there is concern for disease progression and per Investigator discretion in consultation with the Onyx Medical Monitor. If it happens, measurements at the time of addition of new agents will be used as new baseline.

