7.3 Demographic and Baseline Characteristics

The following demographic and baseline characteristics will be summarized by both disease cohorts and overall unless otherwise indicated. Summary statistics will be tabulated based on the Safety population.

- Both Disease Cohorts
 - Age at the entry of PX-171-010: <65, \geq 65
 - Sex: female, male
 - Race: Caucasian, African American, Hispanic, Asian/pacific islander
 - Time since diagnosis (years) in PX-171-010
 - Clinical response assessment at entry of PX-171-010
- MM Cohort
 - Height (cm), weight (kg), body surface area (BSA), ECOG performance status, Neuropathy Grade (All data from time of entry in PX-171-010 except ECOG which is from the time of entry in initial study and entry in PX-171-010.)
 - Number of prior regimens (initial study)
 - Prior Bortezomib (initial study)
 - M-protein light chain isotype and heavy chain isotype (initial study and PX-171-010)
 - Measurable disease category (initial study)
 - Refractory status (initial study)

- Plasma cell involvement (<50%, >=50%) (initial study)
- Cytogenetics (initial study): normal/favorable, poor prognosis, unknown or not done
- FISH (initial study): normal/favorable, poor prognosis, unknown or not done
- Cytogenetics or FISH (initial study): normal/favorable, poor prognosis, unknown or not done
- Serum Beta-2 Microglobulin (mg/L) (initial study)
- Durie-Salmon Staging and Subclassification (initial study)
- Did the subject maintain the parent study's response until PX-171-010 enrollment?
- Did the subject meet IMWG criteria for disease progression until PX-171-010 enrollment?
- Solid Tumor Cohort
 - Tumor type (initial study)

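### For regimens continuing from the parent study, the SAP's ORR is cumulative since the parent-study baseline, but it is not labelled so and has no PX-171-010-only counterpart

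*SAP*

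**What the plan says.** SAP 5.5 sets the baseline. Its first rule applies as follows: "If subjects had not received other anti-cancer therapies and not reached progressive disease when they enrolled in study 010". For these subjects, "baseline disease assessments from the initial study will be used for baseline values for determining response and progression unless no prior assessments were collected". Subjects without a prior baseline (PX-171-008 is the example) are assessed at PX-171-010 screening. For those who enter after progression or other anti-cancer therapy, "baseline values from current study will be used". A later regimen change, such as an added antitumour agent, can reset the baseline again.

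SAP 7.7.4.1 then defines ORR: "Best overall response will be determined by the local investigator for regimens with the common baseline". In myeloma a responder has sCR, CR, VGPR or PR; in solid tumours, confirmed CR or PR. The estimate carries a two-sided 95% Clopper-Pearson interval. The section does not start the assessment window at PX-171-010 entry and does not require a response to be new. For solid tumours, Protocol Appendix E gives the window: "The best overall response is the best response recorded from the start of the treatment until disease progression/recurrence".

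PFS is handled differently. For continuing regimens, SAP 7.7.2 gives a version that starts in the initial study and a second one: "PFS for the period of PX-171-010 study only will be calculated as" time from the first PX-171-010 dose. SAP 7.7.3 makes the same split for TTP. SAP 7.3 lists "Clinical response assessment at entry of PX-171-010" among the baseline characteristics, but the ORR definition does not use it.

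**The concern.** The study objective is the safety and efficacy of long-term or continuing treatment. A response rate reported for this study, with an exact interval, will naturally be read as what extended treatment achieved. For continuing regimens it may instead restate what the parent studies had already achieved.

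The documents expect subjects to enter in response. The Protocol Synopsis (Procedures) describes myeloma subjects entering in PR, VGPR, CR or sCR. Protocol 10.4.2 singles out PX-171-008 subjects as those whose response may first be seen in PX-171-010, which implies that for others it was usually documented earlier. As planned, the ORR cannot show whether continued treatment produced any response beyond those carried in.

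**Working it through.** The documents give no expected ORR, so there is no figure to reproduce. The check has two parts.

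**Does a carried-in response count?** The SAP does not say which assessments feed best overall response, so take both readings.

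- *All assessments since the parent baseline.* This is what the common-baseline wording suggests, and what Appendix E states for solid tumours. A PR reached before enrolment counts.
- *Only PX-171-010 assessments, scored against the parent baseline.* A subject who enters in PR and holds it is still in PR against that baseline, so it counts.

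The readings differ only for a subject who lost a PR before entry without progressing. A response held at entry counts under both.

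**How far can ORR and new response diverge?** Let r be the share of continuing subjects already in PR or better at entry, and q the new-response rate among the rest. Then

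ORR = r + (1 − r) × q.

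With q = 0, ORR = r. The values of r, q and n are assumptions. The documents give only about 100 subjects in total, both cohorts together, so n = 100 is above what any one cohort's continuing group will have. Intervals are exact 95%.

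| r | ORR as planned, q = 0 | New response among those below PR at entry |
|---|---|---|
| 20% | 20/100 = 20.0% (12.7-29.2) | 0/80 (0-4.5) |
| 40% | 40/100 = 40.0% (30.3-50.3) | 0/60 (0-6.0) |
| 60% | 60/100 = 60.0% (49.7-69.7) | 0/40 (0-8.8) |
| 80% | 80/100 = 80.0% (70.8-87.3) | 0/20 (0-16.8) |

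With q = 10% and r = 40%, ORR = 0.40 + 0.60 × 0.10 = 46% (36.0-56.3), against 6/60 = 10.0% new (3.8-20.5).

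Smaller groups widen the intervals but leave the pattern unchanged. At r = 40% and q = 0, n = 70 gives 28/70 (28.5-52.4) against 0/42 (0-8.4). With n = 30 it is 12/30 (22.7-59.4) against 0/18 (0-18.5).

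**Does the ORR exceed the parent-study ORR?** Let p be the parent-study ORR, and a and b the roll-over rates of responders and non-responders. With no new response and every responder still in response at entry,

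ORR among roll-overs = p·a / [p·a + (1 − p)·b].

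If a = b, this equals p and there is no excess. With assumed p = 0.30 and a = 0.50:

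- b = 0.30: 0.15/(0.15 + 0.21) = 41.7%
- b = 0.15: 0.15/(0.15 + 0.105) = 58.8%

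Protocol 1.3 reports one PR among 79 patients in the solid tumour study, so p = 1/79 = 1.3%. The same assumed roll-over rates then give:

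- b = 0.30: 0.0063/(0.0063 + 0.2962) = 2.1%
- b = 0.15: 0.0063/(0.0063 + 0.1481) = 4.1%

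**The case against.** Cumulative best response is a legitimate measure in a roll-over study of continuing treatment. SAP 5.5 states openly that the parent baseline is carried forward, and Appendix E runs best response from the start of treatment. ORR is listed under additional efficacy analyses. It is neither a primary nor a secondary endpoint, no hypothesis is tested and no sample size depends on it. The interval only follows the general rule in SAP 7.1. SAP 7.3 already tabulates response at entry and, for myeloma, whether the parent-study response was maintained until enrolment. PX-171-008 subjects and reset regimens are outside the problem.

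Most of this stands, and it limits the point to a missing label and a missing on-study counterpart. The entry table does not fill that gap. It is a marginal distribution and cannot show which subjects below PR at entry later responded.

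A reader might infer that this ORR must exceed the parent-study ORR, because subjects who do well roll over. The documents do not establish that. Eligibility requires completion of a parent study, not response, and Protocol 1.4 gives maximum parent-study durations from 1 to 18 cycles, so completing a short study says little about response. No roll-over rates are given, and with equal rates there is no excess.

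**Conclusion.** The point holds for regimens that continue from the parent study without a baseline reset. For them, SAP 7.7.4.1 read with SAP 5.5 yields a cumulative ORR that counts responses already held at entry. The SAP separates the on-study period for PFS and TTP but not for ORR.

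The size cannot be derived from the documents. It equals the share in response at entry plus whatever is added on study, and every percentage for that share above is an assumption. An excess over the parent-study ORR needs the further assumption that responders roll over more often. One PR in 79 solid tumour patients suggests that few responses are carried into that cohort, so the issue matters mainly for myeloma.

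Two further inferences should be resisted. Using the parent baseline is not in itself an error. Nor does this undermine a headline result, since ORR is a descriptive additional analysis. The change is still worth making, because without it the study cannot report what extended treatment added to response.

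**What to change.** In SAP 7.7.4.1:

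- Label the continuing-regimen ORR as cumulative (initial study plus PX-171-010) and descriptive of roll-over subjects.
- Add, by disease cohort, a shift table of response at PX-171-010 entry against best response on PX-171-010.
- Report, with an exact 95% interval, the proportion newly reaching PR or better among subjects below PR at entry.
- Present baseline-reset regimens and PX-171-008 subjects separately.

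The cost is one extra table. Response category is already collected at screening, at Cycle 3 and every 3 cycles, and at end of study (Protocol 7.1, 7.6 and 7.7). The on-study figure will have a smaller denominator, hence a wider interval for a given rate, and will probably look less favourable than the cumulative one.
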